## STUDY DESIGN

The study was conducted at the University of Pennsylvania. This placebo-controlled, double-blind, cross-over laboratory study of SmartSleep stimulations included sleep restriction to 5h time in bed for sleep on 4 consecutive nights, preceded by an 8h sleep adaptation night, and followed by a 10h recovery night (Figure 2).

The proposed sample was a total of 12 subjects to be recruited and screened for their ability to engage in the protocol and their similarities to astronauts (e.g., age 30-55y, educational background, healthy, etc.). The protocol involved monitoring of sleep-wake behaviors by actigraphy and sleep diary 2 weeks prior to and 1 week following the 7-day laboratory protocol. Participants were required to remain in the laboratory for the entire 7- day and 6-night protocol for cognitive testing at alarm awakening from sleep (sleep inertia test battery) and throughout each 19h waking period (full Cognition test battery every 4 hours). In addition, participants completed a spatial cognition battery and three tasks with operational relevance to spaceflight (Six Degrees of Freedom, ROBoT, and the Lunar Lander Simulator) once a day. The 6 laboratory nights consisted of a baseline night (8h time in bed [TIB]), 4 nights of 5h TIB (each with one of the four SmartSleep stimulus conditions), and a recovery night of 10h TIB at the end. Each of the 12 subjects received one of the SmartSleep stimulus conditions (Continuous Fixed Interval, Block,

In-Phase Adjustable, and Sham) on one of the 4 sleep restriction nights, according to a balanced orthogonal Latin Square design. This was a fully within-subjects design with high statistical power for the given sample size. This allowed us to investigate how the methodology works across the build-up of chronic sleep restriction (Figure 2).

Subjects	1	2	3	4	5	6	7	8	9	10	11	12
Lab Day 1	Familiarization testing: Cognition performance testing and operational simulation testing											
Night 1 (8h TIB)	Adaptation to SmartSleep cap: sham stim recording nocturnal sleep EEG with no emergent awakening											
Lab Day 2	Cognition performance testing and operational simulation testing											
Night 2 (5h TIB)	Sham	Stim 1	Stim 2	Stim 3	Sham	Stim 1	Stim 2	Stim 3	Sham	Stim 1	Stim 2	Stim 3
	Emergent Awakening (Sleep Inertia Test Bout)											
Lab Day 3	Cognition performance testing and operational simulation testing											
Night 3 (5h TIB)	Stim 1	Sham	Stim 3	Stim 2	Stim 3	Stim 2	Stim 1	Sham	Stim 2	Stim 3	Sham	Stim 1
	Emergent Awakening (Sleep Inertia Test Bout)											
Lab Day 4	Cognition performance testing and operational simulation testing											
Night 4 (5h TIB)	Stim 2	Stim 3	Sham	Stim 1	Stim 1	Sham	Stim 3	Stim 2	Stim 3	Stim 2	Stim 1	Sham
	Emergent Awakening (Sleep Inertia Test Bout)											
Lab Day 5	Cognition performance testing and operational simulation testing											
Night 5 (5h TIB)	Stim 3	Stim 2	Stim 1	Sham	Stim 2	Stim 3	Sham	Stim 1	Stim 1	Sham	Stim 3	Stim 2
	Emergent Awakening (Sleep Inertia Test Bout)											
Lab Day 6	Cognition performance testing and operational simulation testing											
Night 6 (10h TIB)	Recovery sleep: sham stim recording nocturnal sleep EEG with no emergent awakening											

Figure 2: Overview of the study design. Each of the 12 subjects underwent one adaptation night (8h TIB), four sleep-restriction nights (5h TIB), and one recovery night (10h TIB). Each subject was exposed to all four SmartSleep acoustic stimulations on the four sleep restriction nights (Stim1: Continuous Fixed Interval; Stim2: Block; Stim3: In-phase adjustable; and Sham) according to a balanced orthogonal Latin Square design. Subjects performed a sleep inertia test bout consisting of a 3-min. Psychomotor Vigilance Test (PVT-B) and a Digit-Symbol Substitution Test (DSST) after emergent awakenings. They also performed cognitive and operational testing throughout the wake periods.

The following cognitive and spaceflight-relevant operational tasks were administered throughout the waking period on all days of the protocol (Figure 3):

[figure not shown]

Figure 3: Schematic of study timeline including the sampling frequency of cognitive performance and

*spaceflight operationally relevant task assessments. Black rectangles signify sleep periods with the nightly sleep opportunity presented in white text and wake periods are interspersed between each sleep period. Time of day is displayed along the bottom of the laboratory protocol timeline. Cognitive and spaceflight relevant operational tasks that were administered together are grouped and color-coded; each test grouping is associated with a colored arrow and all test administrations are positioned along the study timeline. Cognition, which included a DST, is colored blue; a short cognitive test battery comprised of the PVT, DSST, and DST are colored green, spaceflight operational tasks (ROBoT, 6DF, and Lunar Lander) are colored pink, and spatial cognition is colored gray. Sleep inertia test bouts were administered upon awakening after each sleep restricted night and are identified with text above the blue Cognition arrow. Descending subtraction Task (DST); Brief Psychomotor Vigilance Test (PVT); Digit-Symbol Substitution Test (DSST) after emergent awakenings.*

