The Cognition battery (Basner et al., 2015; Moore et al., 2017) was administered on calibrated laptop computers. On average, 5 ISS astronauts required only 16.5 min to answer a brief survey followed by their performance on the 10 Cognition tests. We have generated software that automatically extracts key Cognition accuracy and speed outcomes. Facilitating our large database of Cognition tests, we determined loading and difficulty of individual stimuli via Item Response Theory (Embretson and Reise, 2000), which increases the power for our analyses relative to analyses based on standard accuracy outcomes (e.g., percent correct). The data analysis process was as follows: (1) extract one key accuracy and speed outcome for each test; (2) correct outcomes for practice and stimulus set difficulty effects; and (3) standardize outcomes based on baseline performance of all subjects (we will also generate speed, accuracy, and efficiency scores across cognitive domains).

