## **STATISTICAL APPROACH**

We conducted a randomized, double-blind, cross-over laboratory study on the effects of the slow-wave enhancing smart sleep technology on cognitive performance during 4 consecutive nights of sleep restriction (5h time in bed). We compared the four auditory stimulation modalities (continuous fixed interval, block, in-phase adjustable, and sham) relative to their slow-wave and performance enhancing properties. Each subject was exposed to all 4 modalities (within-subject study design). We used a balanced orthogonal Latin Square design (i.e., each stimulus modality will appear in each of the 4 sleep restriction nights exactly once, and each modality will be preceded by each other modality exactly once).

Cognitive test data were standardized to baseline performance. We used linear mixed effect models (in SAS version 9.4, SAS Institute, Cary, NC) with random subject intercept to account for the clustered nature of the data. The model included factors for stimulus modality (4 levels), sleep restriction night (4 levels), and their interaction. We were both interested in the main effects (modality and sleep restriction) and their interaction, but acknowledge the limited power for detecting a significant interaction. If the type-III fixed effect estimate indicates a significant difference between groups, we compared them in post-hoc tests. The primary outcome was the number of lapses (errors of commission; response times >355 ms) on the brief Psychomotor Vigilance Test (PVT-B) after emergent awakenings and during the day. Performance on the Digit Symbol Substitution (DSST), Descending Subtraction Task (DST), and spaceflight relevant task (ROBoT) were treated as secondary outcomes. The other cognitive tests (Cognition, Spatial Cognition, tasks with operational relevance for spaceflight) were treated as tertiary outcomes. Statistical tests for secondary and tertiary outcomes were adjusted with the false discovery rate method (Curran-Everet, 2000).

For the power calculations (Figure 4), we assumed a correlation between measurements of 0.8, and varied the standard deviation of the difference between modalities/sleep restriction nights from 0.8 to 1. We expect to have >80% power to find a medium effect size of 0.5 statistically significantly different for standard deviations <0.9.

[figure not shown]

Figure 4: Power calculations

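### The modality-by-night (build-up) contrasts are partly between subjects and weakly powered, and the model omits each subject's own pre-restriction value, which would recover a small part of the loss

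*Combined protocol and SAP*

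**What the plan says.** The Study Design section of the combined protocol and SAP states: "This was a fully within-subjects design with high statistical power for the given sample size". The next sentence presents this as what made it possible to study the technology over accumulating restriction, which is the subject of Specific Aim 4. On sample size it says "The proposed sample was a total of 12 subjects to be recruited and screened".

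The Statistical Approach describes the Latin square arrangement, in which "each stimulus modality will appear in each of the 4 sleep restriction nights exactly once". The model has modality, night and their interaction as fixed effects and a random subject intercept. The authors "acknowledge the limited power for detecting a significant interaction" but give no figure for it. The power statement is "We expect to have >80% power to find a medium effect size of 0.5 statistically significantly different for standard deviations <0.9", and for it "we assumed a correlation between measurements of 0.8".

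On baseline, the Cognition Test Battery section says the process is to "standardize outcomes based on baseline performance of all subjects". The Statistical Approach says only that cognitive data were standardised to baseline, without saying whether this means the subject's own baseline or the group's. No baseline term is listed in the model. Figure 2 shows performance testing on Lab Day 2 and a sham EEG recording on Night 1, both before restriction begins. Night 1 has no emergent awakening.

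**The concern.** Aim 4 asks whether the stimulation effect changes as restriction accumulates, so it rests on the modality-by-night interaction. Each subject has sham on one night only. On any given night, stimulation and sham are therefore seen in different people, and part of the information on how the effect varies by night carries between-subject variance.

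A reader of the Study Design section alone would take the high-power claim to cover this question. A null Aim 4 result could then be read as evidence that the effect does not change over nights, when the trial had little chance of detecting such a change. Data that would remove some of the between-subject variance are already collected, yet the model does not use them as a covariate.

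**Working it through.** **Inputs.** 12 subjects and the 12 sequences of Figure 2 (Study Design); correlation 0.8, effect 0.5 and SD 0.8 to 1 (Statistical Approach). Assumed, because not stated: two-sided 0.05 and no dropout.

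**1. The plan's own figure.** A paired t-test with n = 12 and SD of the difference = SD × √(2 × (1 − 0.8)) gives power of 87.5% at SD 0.8, 83.4% at 0.85, 79.1% at 0.9 and 70.4% at 1.0. This agrees closely with the stated >80% below 0.9, provided the SD is that of one measurement. Read literally as the SD of a difference, it gives 50.6% at 0.8 and 42.0% at 0.9. The single-measurement reading is used below. The figure concerns one modality against sham, pooled over nights.

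**2. Allocation.** In Figure 2, sham falls on subjects 1, 5, 9 (Night 2); 2, 8, 11 (Night 3); 3, 6, 12 (Night 4); and 4, 7, 10 (Night 5). Every night is 9 stimulated against 3 sham.

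**3. Information in the planned model.** Take SD 1, so subject variance is 0.8 and residual variance 0.2. Consider contrasts of the 16 modality-by-night cells, scaled so that squared coefficients sum to 1. Each of the three squares observes every cell once.
- Main effects are within-subject in all three squares: information 3/0.2 = 15, variance 0.0667.
- Interaction contrasts are within-subject in two squares and confounded with subjects in the third: information 2/0.2 + 1/(0.2 + 4 × 0.8) = 10 + 0.294 = 10.294, variance 0.0971.

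**4. Standard errors** (three modalities averaged, minus sham).
- Averaged over nights (squared coefficients sum to 1/3, all main effect): variance 0.0667/3 = 0.0222, SE 0.149.
- Night 5 (1/3 main effect plus 1 interaction): 0.0222 + 0.0971 = 0.1194, SE 0.3455, which is 2.3 times larger. Every other night gives the same.
- Linear change per night (4/15, all interaction): 0.0259, SE 0.1609.
- Night main effect, Night 5 minus Night 2 (1/2, all main effect): 0.0333, SE 0.183.

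Generalised least squares on the 48 subject-nights gives the same Night 5 value.

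**5. Power for a 0.5 difference** (noncentral t, 21 df).

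| SD | Averaged over nights | Night 5 |
|---|---|---|
| 1.0 | 89% | 28% |
| 0.9 | 94% | 34% |
| 0.8 | 98% | 41% |

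For a linear trend totalling 0.5 from Night 2 to Night 5, power at SD 1 is about 17%.

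**6. Where the loss comes from.** One night's data alone (9 v 3) give SE √(1/3 + 1/9) = 0.667. The random intercept brings this to 0.3455. If no between-subject variance remained, interaction information would also be 15 and the Night 5 SE would be √(0.0222 + 0.0667) = 0.298, exactly twice 0.149. Most of the 2.3-fold ratio thus reflects one night holding a quarter of the data; the between-subject part is the step from 0.298 to 0.3455.

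**7. Adding own baseline, correlation 0.8 assumed.** Remaining subject variance is 0.8 − 0.8² = 0.16. Interaction information becomes 10 + 1/(0.2 + 4 × 0.16) = 11.190, variance 0.0894.
- Night 5: 0.0222 + 0.0894 = 0.1116, SE 0.334 (3% lower; 0.1194/0.1116 = 1.07). Power goes from 28% to 30%.
- Trend: SE 0.1544 (4% lower; 0.0971/0.0894 = 1.09). Power for a total change of 0.5 goes from about 17% to 18%.
- Main effects: unchanged.

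At SD 0.9 (normal approximation), Night 5 power goes from 18% to 19% if all correlations are 0.5, and from 62% to 65% if they are 0.9.

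**8. If own-baseline change scores are already used.** Subject variance becomes 0.2, information is 10 + 1/(0.2 + 4 × 0.2) = 11, and the Night 5 SE is 0.336. The covariate then adds almost nothing.

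**The case against.** The strongest reply is that the plan already admits the weakness. The Statistical Approach concedes limited interaction power, and the Study Design section says only that the design allowed build-up to be investigated. Calling a crossover fully within-subject is ordinary usage when every subject receives every condition. That stands: the wording change mostly carries an existing caveat to the place where the claim is made.

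It is also fair that the random intercept already recovers most of the loss, so the missing covariate is not what makes Aim 4 weak. The covariate is worth 1-2 power points at the plan's own effect size, and the ratio of Night 5 to averaged SE is still 0.334/0.149 = 2.2 with it.

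Three stronger readings are tempting and not supported:
- **That all comparisons across nights are between subjects.** Every subject is measured on all four restriction nights, so the night main effect is wholly within-subject. Modality-by-night contrasts are only partly between subjects and can be estimated from within-subject information.
- **That baseline enters every outcome only as a group rescaling.** The reference to all subjects describes the Cognition battery. The Statistical Approach leaves own or group baseline open for the rest.
- **That a baseline covariate would help every primary outcome.** Lapses after emergent awakening have no matching baseline. For slow waves, the baseline comes from an 8h night, and its correlation with 5h nights is not given.

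**Conclusion.** The point holds as a minor one. The high-power claim is sound for modality and night main effects on the plan's assumptions. It does not extend to the modality-by-night contrasts, where power for a 0.5 difference on a single night is about 28% to 41% over SD 1 to 0.8. Leaving out each subject's own pre-restriction value forgoes about 7-9% of the information on these contrasts for daytime and slow-wave outcomes. This is a small, nearly free gain in precision and does not rescue Aim 4.

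A reader might infer that the plan conceals the low power or that the missing covariate causes it. Neither follows: the limitation is conceded, and it comes mainly from the design and sample size.

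The figures rest on equal correlation of 0.8 between nights, the same correlation with baseline, SD read as that of one measurement, two-sided 0.05 and no dropout. The gain is smaller with a weaker baseline correlation, or if own-baseline change scores are already analysed.

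**What to change.** 1. In the Statistical Approach, for daytime and slow-wave outcomes, add each subject's own pre-restriction value to the mixed model as a covariate: Lab Day 2 performance on the same measure, or the Night 1 sham EEG value. State whether standardisation uses own or group baseline. Leave the emergent-awakening model as it is.
2. In the Study Design section, confine the high-power statement to the modality and night main effects. For the modality-by-night interaction only, cross-refer to the limited-power statement in the Statistical Approach.

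The cost is one between-subject degree of freedom and a sentence or two of text. No new data are needed. If results have already been seen, the covariate model should be reported beside the planned one and identified as added later.

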### **Sleep Inertia Test Bout**

The Sleep Inertia Test Bout was administered at the time of emergent awakenings, and consisted of two measures that were developed and validated to be sensitive to sleep inertia: the Brief Psychomotor Vigilance Test (PVT-B) to assess behavioral alertness and psychomotor speed (Basner et al., 2011); and the Digit Symbol Substitution Test (DSST) to assess cognitive processing throughput. In addition, we administered the Descending Subtraction Task (DST), a validated measure of working memory sensitive the effects of sleep loss and sleep inertia (Dinges, 1990; Dinges et al., 1985), as well as Visual Analog Scales (VAS) to assess subjective ratings of mental fatigue, tiredness, physical exhaustion, level of stress, sleep quality, and sleepiness.

The PVT-B is a well-validated test based on vigilant attention and reaction time (Basner & Dinges, 2011; Lim & Dinges, 2008). Subjects are instructed to monitor a rectangular box on the screen and press the space bar as quickly as possible each time a millisecond counter appears. Each PVT-B reaction time is displayed for one second as feedback. Subjects are asked to respond as quickly as possible without committing false starts in the absence of stimuli.

The 1.5-minute Digit Symbol Substitution Test (DSST) is validated to be sensitive to fatigue from sleep loss (Van Dongen et al., 2003; Dinges et al., 1985). The test is based on the original version in the Wechsler Adult Intelligence Scale. Subjects are presented with a legend that pairs unique symbols to digits (1 through 9). Symbols are then sequentially presented on the screen in random order. Subjects are instructed to press the corresponding number key as soon as possible. On each test administration, the symbol and digit correspondence is randomly reassigned. The DSST measures cognitive throughput based on perception and memory.

The Descending Subtraction Test (DST) is a measure of working memory that is sensitive to fatigue from sleep loss and sleep inertia (Dinges, 1990; Dinges et al., 1985). The DST requires participants to mentally subtract numbers in a sequential fashion as quickly as possible. For example, if the starting number is 987, the participant subtracts nine from 987, with the difference being 978, the participant then subtracts eight from 978, and so on subtracting by seven, six, five, four, three, and two, from each difference at which point, the participant then recycles the subtraction sequence beginning at nine again. The DST was two minutes in duration and responses were entered on a keyboard.

The Visual Analog Scales (VAS) measured subjective ratings with end points of “Mentally Sharp” (0) and “Mentally Fatigued” (10); “Tired” (0) and “Fresh, Ready to Go” (10); “Energetic” (0) and “Physically Exhausted” (10); “Not Stressed At All” (0) and “Very Stressed” (10); “Low Sleep Quality” (0) and “High Sleep Quality” (10); and “Not Sleepy At All” (0) and “Very Sleepy” (10).

### **Cognition Test Battery**

Cognition was developed for spaceflight by [name] and his team at the University of Pennsylvania (Basner et al., 2015; Moore et al., 2017). It consists of 10 brief neuropsychological tests that cover a range of cognitive domains that are relevant for spaceflight and go beyond what is measured with NASA’s standard WinSCAT test battery (e.g., emotion recognition and risk decision-making). Fifteen unique versions of each test allow for repeated

administration of the battery. Importantly, a ground-based study in N=46 astronaut surrogate subjects allows for correcting for practice effects and stimulus set difficulty effects. Links to cerebral networks have been established with fMRI (Roalf et al., 2014). The battery was specifically designed for the high-performing astronaut population and was validated in both astronaut and astronaut surrogate populations on the ground and on the ISS (Moore et al., 2017). Overall, the battery has been administered 7,222 times in 720 unique subjects (mean age 35.1 years, SD 9.0 years, range 20-62 years; 71% male), including 5 astronauts on 6-month ISS missions, 2 astronauts on 12-month ISS missions, 8 astronauts in a ground-based study at Johnson Space Center (JSC), and 198 subjects in several space analog environments (including head-down tilt bed rest, HERA, and Antarctic research stations). The sensitivity of the battery to environmental stressors typically encountered on the ISS (e.g., sleep deprivation and high levels of CO2 [Basner et al., 2017]) has been established. Furthermore, we demonstrated that a subset of 3 Cognition tests (Digit Symbol Substitution, Abstract Matching, and Fractal 2-Back) was able to predict 30% of 6DF-docking performance variance on a task that is regularly used on the ISS (Johannes et al., 2016). Finally, Cognition is part of ISS Standard Measures. Therefore, Cognition constitutes a well-established and validated instrument for measuring spaceflight effects on cognitive performance.

The Cognition battery (Basner et al., 2015; Moore et al., 2017) was administered on calibrated laptop computers. On average, 5 ISS astronauts required only 16.5 min to answer a brief survey followed by their performance on the 10 Cognition tests. We have generated software that automatically extracts key Cognition accuracy and speed outcomes. Facilitating our large database of Cognition tests, we determined loading and difficulty of individual stimuli via Item Response Theory (Embretson and Reise, 2000), which increases the power for our analyses relative to analyses based on standard accuracy outcomes (e.g., percent correct). The data analysis process was as follows: (1) extract one key accuracy and speed outcome for each test; (2) correct outcomes for practice and stimulus set difficulty effects; and (3) standardize outcomes based on baseline performance of all subjects (we will also generate speed, accuracy, and efficiency scores across cognitive domains).

